The scientific premise underpinning this research is that a theory-based, family-centered intervention focused on skill building, improved family context, and problem-solving will improve SS physical function and quality of life while reducing CP negative outcomes during outpatient rehabilitation. The research design is a mixed methods, two-group (2:1) exploratory pilot study comparing intervention (CARE-CITE with usual customary care (n=24 dyads) to an attention control with usual customary care (n=12 dyads).

Aim 1: To evaluate effects of web-based CARE-CITE at home during subacute stroke recovery on both CP and SS health outcomes and QOL. *Hypotheses: 1.1. CPs receiving CARE-CITE will have reduced depressive symptoms and improved QOL at 2-month post intervention compared to the control group. 1.2. SSs receiving CARE-CITE will have improved upper extremity function and QOL at 2-month post intervention compared to the control group.*

Aim 2: To examine the effect of web-based CARE-CITE on the family context and processes related to stroke rehabilitation. *Hypotheses: 2.1. CPs receiving CARE-CITE will have less family conflict and provide greater autonomy support at 2-month post intervention compared to the control group. 2.2. SSs receiving CARE-CITE will have improved perceived autonomy support and UE self-efficacy at 2-month post intervention compared to control group.*

Exploratory Aim. Use qualitative methods to complement the interpretation of effects on processes and outcomes from Aims 1 and 2. At 3 months post intervention, we will evaluate CPs' perceptions of the benefits, challenges and experiences with the intervention and explore changes in their perceived QOL, family conflict, and autonomy support.

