Inclusion/exclusion criteria: All SSs will be 1-3 months post ischemic or hemorrhagic event¹⁰, discharged from inpatient neurologic rehabilitation to their home, have minimal to moderate UE deficits (actively initiate 20 degrees of wrist and 10 degrees of finger extension), no severe cognitive deficits (Mini-mental test¹¹ >24), no physician determined major medical problems that would limit participation in outpatient therapy, and a CP living in the home.^{10, 12} CPs must >21 years old, able to read and write English and have no significant cognitive deficits (Mini-mental test >24). CPs will be defined as those individuals who are a spouse/partner or family member dwelling in the same household, the family member most involved in stroke recovery, and self-identify as the primary caregiver of the SS.^{4, 13} CPs must be familiar with using a computer and accessing websites, or be familiar with using a tablet (available for loan if no computer available).

We plan to recruit 12 dyads into the usual care attention control group and 24 dyads into the CARE-CITE group. The larger intervention group will contribute precision to the pilot-based estimates of mean changes and variability for key outcomes, while also improving the lessons to be learned about feasibility to inform future implementation for a larger-scale trial. Given the PI's extensive and successful recruitment experience for other prior stroke studies, a recruitment rate of 2-3 dyads per month is a realistic estimate for the proposed time period. An attrition rate of ~8% is projected based on the literature;¹⁴⁻¹⁶ thus, we will enroll 40 dyads to achieve a complete sample of 36.

Intervention group: CARE-CITE: While the SS is receiving usual and customary outpatient UE rehabilitation, the CARE-CITE intervention will occur over 4 weeks. The primary CARE-CITE components will be education via web platform. The research interventionist will conduct a virtual in-home visit via Emory Zoom platform at orientation and during week 4, and telephone follow ups. The research interventionist will work in tandem with the outpatient rehabilitation treatment team to coordinate care plans and patient goals.

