1) Visit 1: Virtual Orientation (3 hours). The research interventionist will meet virtually with CP and SS to review collaborative goals setting, evaluate UE movement limitations, and identify functional activity preferences. Together, they will begin development of a progressive therapeutic exercise plan for home-based functional task practice, determine activities for each goal and measurable milestones to accomplish during the treatment period, creating a framework to improve joint responsibilities for self-management skills.

2) CP completes 6 online CARE-CITE modules (15-30-minute sessions each). During the week following Visit 1, the CP will access the website to complete 6 online modules. Modules include demonstration videos and instructive content covering following areas: principles of functional task practice (i.e., activities of daily living such as eating, grooming, or leisure/vocational activities), adaptation of tasks, and importance of progression of challenging tasks to drive neuroplasticity (i.e., increasing numbers of practice repetitions or weight of objects lifted). Examples are provided to address potential SS frustration and improve adherence. Underpinning the content is the concept of autonomy support, with examples of fostering empathy (e.g., the CP using non-dominant hand during activities), problem solving (guidance for adaptation of functional activities at home to increase success or challenge), instruction in the use of non-controlling language with role playing situations and the importance of creating choice in activities. For example, in one vignette to demonstrate problem solving, a CP interacts with the SS during a meal using non-controlling language to offer choice for task modifications for manipulating food with the weaker hand. The SS becomes frustrated with the challenging task, and the CP demonstrates options for dialogue that foster collaborative problem solving.

3) Weekly teleconference/Zoom check-in. Each week during the 4-week intervention, the research interventionist will complete a structured 10-minute phone call with CP to answer questions and assist with problem solving.

4) Visit 2: Virtual Home visit (3 hours). At the end of week 4, the same research interventionist will conduct a virtual home visit to review progress with milestones and advancement of activity goals.

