5) **"CARE-CITE Booster" session** – 4 weeks after the intervention period, the research interventionist will make a brief 10-minute telephone booster call to reinforce CARE-CITE content, ask the CPs to identify two challenging areas during SS practice activities, and CP opportunities to use principles of autonomy support.

Attention Control group: SS and CP will receive customary care outpatient rehabilitation therapy but no CARE-CITE intervention. The CP will receive a CP support brochure with general caregiving information including website resources to mimic web interaction of intervention group (e.g., stroke caregiver resource site). The research coordinator will handle all communication. The CP will receive the same number of structured weekly phone calls and the "booster call" to answer any questions, assess helpfulness of the information and ascertain if there was any use of the web resources or social support groups.

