Procedures: The research coordinator will make a virtual screening appointment at via HIPPA compliant Emory Zoom telehealth platform for interested participants. If screening criteria are met, an electronic informed consent (via RedCAP data management system) will be obtained from the CP and SS. Following baseline data collection obtained via a virtual evaluation by the research evaluator (licensed physical therapist), participants will be randomized to groups using a random number generator. The research interventionist (licensed physical therapist) will schedule dyads in the intervention group for the orientation virtual home visit and the second virtual home visit and complete weekly phone calls. The research coordinator will schedule all dyad data collection appointments and complete attention control group dyads phone calls. All dyads complete a virtual evaluation for the 3-month post-test visit. *To increase rigor and minimize bias*, data collectors will be blinded to group assignment/study hypotheses and will be trained in study procedures (e.g. Mini-mental test administration) by the PI [[name]], with regular assessments of competence every 4 months. The PI will train the research interventionist in delivering the intervention and provide supervision by reviewing all in home visits. To minimize missing data, all participants will be sent email / text / mail reminders for upcoming appointment dates. Using the web platform, we will be able to track the frequency and time on each web module. All dyads will receive \$100 for study participation at the end of the 3-month follow up.

Instruments: Variables and measures have all been tested in this population previously. Each standard tool has evidence of established reliability and validity in this patient population as referenced in **Table 2**.

Table 2. R21 Measures collected at baseline and 3 months post-intervention

VARIABLE	MEASURES	Description	Reliability/Validity
CP Depression	CES-D	20-item, Likert-type scale	Established validity, internal consistency, reliability ¹⁷
CP Quality of life	SF-36	36-item Likert-type scale, mental health domain	Sensitive indicator CP mental health ^{18, 19}
SS Quality of Life	Stroke Impact Scale (SIS)	59-items, 8 domains function	Test-retest reliability ICC = 0.70 to 0.92; Internal consistency alpha coefficient of 0.83-0.90 ²⁰

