Data Management and Planned Analysis: All quantitative data storage will be maintained through the Emory HIPPA compliant REDCap database. Standard data cleaning, identification of missing data, identification of outliers, and internal consistency reliability for standardized scales will be completed. Initial data analysis will include descriptive statistics to describe the sample and summarize major study variables. **For Aim 1**, we hypothesize that for dyads receiving CARE-CITE, CPs will display reduced (improved) CES-D depression and improved SF-36 (QOL) scores and SS will have higher scores on the MAL (improved use of arm function), SIS (QOL), and reduced scores on the WMFT (faster UE speed of movement) consistent with moderate to large effect sizes at 3-months as compared to baseline and more favorable changes in these scores after 3-months as compared to the attention control group. **For Aim 2**, we hypothesize that for dyads receiving CARE-CITE, both members will have higher autonomy support (FCCQ-CP; FCCQ-SS), CP will have reduced FCCS (family conflict) and SS will display higher CAHM (UE self-efficacy) as compared to baseline and to the control group. The first component of the primary analysis will involve the construction of 95% confidence intervals in order to summarize changes from baseline to 3-months within each group. We will also report the results of paired t tests or nonparametric Wilcoxon signed rank tests to assess changes from baseline to two months post intervention within each group. Similarly, we will compare mean or median changes of the outcomes targeted in Aims 1 and 2 across the two groups using two-sample t tests or Wilcoxon rank sum tests, respectively. Recognizing the pilot nature of the study, these inferences will be viewed primarily as descriptive rather than as definitive hypothesis testing efforts. To address the multidimensional nature of the data, we will examine inter-correlations among the study variables, including variables that may influence response to the intervention. As needed, we will use linear regression models to augment the primary analyses in order to assess the extent of association between patient characteristics and mean changes and whether observed differences in mean changes across groups persist after controlling for such variables. The **biological variables** of CP age, sex, gender and relationship of CP to SS (e.g. spouse, adult child) and other participant characteristics such as SS other health problems will be examined and potential relationships explored to gain insight into possible confounding factors. **Potential limitations:** While CP of any sex/gender will be recruited, most CPs are female, which may limit interpretations of any sex/gender differences found.

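### Does the attention-control label misdescribe the comparison, given that only the number of calls is matched?

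*Combined protocol and SAP*

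**What the plan says.** The opening design statement compares CARE-CITE with usual care "to an attention control with usual customary care (n=12 dyads"). The recruitment paragraph calls the same arm the "usual care attention control group". The Procedures section has the research coordinator "complete attention control group dyads phone calls", and Data Management and Planned Analysis looks for "more favorable changes in these scores after 3-months as compared to the attention control group".

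The section on the intervention group gives the CARE-CITE schedule:

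- "Visit 1: Virtual Orientation (3 hours"), held with both the care partner and the survivor;
- six web modules for the care partner;
- each week for four weeks, a "structured 10-minute phone call with CP";
- "Visit 2: Virtual Home visit (3 hours") at the end of week 4;
- a 10-minute booster call four weeks after the intervention period.

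A physical therapist delivers the live contact and also coordinates plans and goals with the survivor's outpatient team.

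The Attention Control group section gives controls their customary outpatient therapy, a brochure with web resources intended as a counterpart to the web exposure, and calls: "The CP will receive the same number of structured weekly phone calls", with a booster as well. The coordinator makes these calls, and their length is not stated. The section describes no counterpart to the two long sessions or to the coordination with the outpatient team.

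**The concern.** An attention control normally receives similar contact without the active content, so that a difference between arms can be credited to the content. Here most of the live contact falls in one arm. A reader who relies on the label could take a difference in depression, quality of life, arm use or self-efficacy as already net of therapist time, and could credit it to the web modules or to autonomy support.

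Outpatient therapy raises a second worry. It is background treatment in both arms, but study staff coordinate with the treating team in only one. Its amount is not named in Table 2, among the secondary measures, or in the list of additional clinical data. If coordination changed the therapy received, the pilot has no stated plan to show it.

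**Working it through.** The plan states no total contact time for either arm, so there is no figure of its own to reproduce. The totals below use the session counts and lengths in the intervention and control sections. Evaluations common to both arms and home practice are left out.

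**CARE-CITE, live contact with the care partner**

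- Two sessions: 2 × 180 = 360 min
- Weekly calls: 4 × 10 = 40 min
- Booster: 1 × 10 = 10 min
- Total: 360 + 40 + 10 = 410 min
- Share in the two sessions: 360 / 410 = 87.8%

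**Control, live contact with the care partner** (4 weekly calls + 1 booster = 5 calls; the length is assumed)

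| Assumed minutes per call | Control total (min) | Share of 410 | Shortfall (min) |
|---|---|---|---|
| 5 | 25 | 6.1% | 385 |
| 10 | 50 | 12.2% | 360 |
| 30 | 150 | 36.6% | 260 |

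Equal live time would need 410 / 5 = 82 minutes per control call, so no plausible call length closes the gap.

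**Survivors.** The calls go to the care partner in both arms, so the totals above do not apply to survivors. The first session includes the survivor; the protocol does not list who attends the second. Survivor contact in CARE-CITE is therefore 180 to 360 minutes. None is described for control survivors outside evaluations.

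**What the contrast is asked to estimate.** Aims 1 and 2 ask for the effect of CARE-CITE on outcomes and on family processes. The two sessions are part of CARE-CITE: they carry goal setting, assessment of arm movement, planning of home practice and review of milestones. Their 360 minutes are treatment, and do not count simply as unmatched attention. Any change in outpatient therapy brought about by coordination would likewise be a pathway of the package. Neither biases the randomised package comparison.

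**Where mechanism is addressed.** Research Design and Methods sets out to gather evidence on mechanisms. The Aim 2 process measures (autonomy support, family conflict, self-efficacy) and the interviews supply it. In Exploratory Aim Methods, the mechanism work sets score changes beside themes from interviews with care partners in the intervention group only. No section says that the difference between arms will be used to attribute effects to one component.

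**What the outpatient-therapy count would add.** The protocol describes coordination of plans and goals, not of amount. Visits and minutes could stay equal while content changed. With 24 and 12 dyads, and with records that may be incomplete for therapy delivered elsewhere, counts by arm would be weak evidence either way. They can already be collected: Study Participants provides for medical record review, and the clinical data list under Instruments is open-ended.

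**The case for a change.** The strongest case for a change has three parts.

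First, the imbalance is greatest for survivors, who have no described live control contact outside evaluations, although Hypotheses 1.2 and 2.2 concern them. With the Wolf Motor Function Test dropped from the remote study, the survivor measures left in Table 2 are questionnaires or rating scales, for which attention is a credible rival explanation.

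Second, the aims describe CARE-CITE as web-based, and the protocol presents web education as the primary component. Yet the two sessions total 360 minutes against 6 × 15 = 90 to 6 × 30 = 180 minutes of modules. The wording invites the reader to credit the web content.

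Third, the plan's statement that its inferences are mainly descriptive concerns how firm they are, not what they estimate.

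All three points are accurate, and they limit interpretation: a difference between arms cannot be divided into content, therapist time and attention. They do not show a fault in the planned analysis. To say the comparator does not control for attention at all would also go too far, since call frequency is matched and the brochure with web resources is a deliberate, if modest, counterpart to the modules. The label is generous, but the paragraph beneath it states exactly what controls receive, and the recruitment paragraph couples it with usual care.

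**Conclusion.** The facts behind the concern are correct, but no change to the plan follows. The comparator is a partial attention match: of 410 scheduled live minutes for CARE-CITE care partners, 360 (88%) have no control counterpart. The control total is 50 minutes at an assumed 10 minutes per call, or 25 to 150 minutes over an assumed range of 5 to 30.

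The plan as written still gives a sound descriptive comparison of the whole CARE-CITE package with usual care plus a brochure and calls, which is what Aims 1 and 2 need from an exploratory pilot. New terminology would change no estimate, interval, test or sample size. Authors of the report can describe the contrast as a package effect from the protocol as it stands, and can summarise outpatient therapy by arm where records allow. Such a summary should stay descriptive, because therapy after randomisation may be part of the effect.

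This conclusion assumes that the arm comparison is not later presented as evidence that one component, net of contact time, caused a difference. The documents do not propose that reading.

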- **General Overview of Proposed Methods:** We propose a mixed methods, convergent design⁹ with a two-group experimental approach with separate quantitative and qualitative analyses followed by integration of the findings. We will block randomize (2:1) 36 dyads to treatment or control. All SS will be 1-3 months post stroke and living at home to capture family dyads who are still in sub-acute post stroke outpatient rehabilitation therapy. The intervention will last 4 weeks. Baseline and 3-month post-intervention assessments will include questionnaires, measures of recovery, and semi-structured interviews (**Table 2**). **Methodological Modification:** All study interactions with participants (including screening, evaluations and interventions) will occur remotely via phone call or HIPPA compliant Zoom platform currently being used by Emory Healthcare for telehealth clinic visits.

Study Participants: All Emory Hospital stroke admissions will be screened based upon study

inclusion/exclusion criteria and contacted by the research coordinator, if eligible. Participant eligibility will be confirmed via telephone and virtual screen, and initial virtual evaluation will follow. All self-report written CP and SS questionnaires will be delivered to participants' homes for completion. Completed questionnaires will be returned via self-addressed stamped envelope or study staff will arrange for pick-up from the participant's home. The evaluator will review questionnaires for completeness and conduct a virtual evaluation to complete SS upper extremity assessments and address any missing CP data. All potential dyads will read/sign Emory IRB approved consent/HIPAA forms. Evaluations and training sessions will be video-recorded for standardization procedures to ensure study rigor and reliability. Video or audio recording is optional and not required for participants to participate in the study. Participants will have the option to consent to these recordings. A medical screen from participant's physician will be obtained prior to enrollment. Patients will agree to allow researchers to review their medical records for data collection.

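### Paired tests run separately in arms of 24 and 12 favour CARE-CITE when both arms change equally, and the plan does not make the between-arm difference the basis for an effect

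*Combined protocol and SAP*

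**What the plan says.** The section Data Management and Planned Analysis of the combined protocol and SAP names as the first component of the primary analysis "the construction of 95% confidence intervals in order to summarize changes from baseline to 3-months within each group". It continues: "We will also report the results of paired t tests or nonparametric Wilcoxon signed rank tests to assess changes from baseline", again within each group. A two-sample t or rank sum comparison of changes between arms follows, with regression adjustment as needed. The section describes all of these inferences as mainly descriptive because the study is a pilot.

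The same section words the Aim 1 hypothesis for CARE-CITE dyads as results "consistent with moderate to large effect sizes at 3-months as compared to baseline", joined to more favourable change than in the control group. Aim 2 is likewise set against both baseline and control. The formal hypotheses listed under Aims 1 and 2 at the start of the protocol (1.1, 1.2, 2.1 and 2.2) are stated against the control group only.

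On size: "We will block randomize (2:1) 36 dyads to treatment or control", and under Inclusion/exclusion criteria, "We plan to recruit 12 dyads into the usual care attention control group and 24 dyads into the CARE-CITE group". On setting: "All SS will be 1-3 months post stroke and living at home", and for the control arm, "SS and CP will receive customary care outpatient rehabilitation therapy but no CARE-CITE intervention".

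**The concern.** A paired test asks whether one arm changed. It does not ask whether the arms changed by different amounts. Survivors at this stage, all in outpatient rehabilitation, may well improve in both arms, so a significant change in the CARE-CITE arm does not show that CARE-CITE caused it.

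Unequal arms make this worse. With twice the sample, the CARE-CITE test detects the same true change more often. A results table could then show a significant change under CARE-CITE and a non-significant one under control for no reason other than arm size. Calling the tests descriptive limits how strongly such a pattern may be stated, but does not change the direction in which it leans. The pilot is meant to inform a larger trial, and a pattern of this kind could be carried forward as a sign of efficacy.

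**Working it through.** **The plan's own figure.** The only sample-size arithmetic is the enrolment target: 36 / (1 − 0.08) = 39.1, rounded up to 40, as stated. No power or significance level is given for any test.

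**Inputs.**
- Arm sizes 24 and 12: from the plan.
- Two-sided 5% level: assumed, to match the planned 95% intervals.
- Standardised change d = mean change / SD of change, the same in both arms (no CARE-CITE effect), with equal SDs: assumed. The documents give neither the size of natural recovery nor an SD, so d is shown as a range.

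**Formulas.** The power of a paired t test with n dyads is P(|T| > t(0.975, n − 1)), where T is noncentral t with n − 1 degrees of freedom and noncentrality d√n. The critical values are 2.069 for n = 24 and 2.201 for n = 12. The arms are independent, so with powers p24 and p12:
- CARE-CITE only = p24 × (1 − p12)
- control only = p12 × (1 − p24)
- both = p24 × p12

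For d = 0.6, p24 = 0.804 and p12 = 0.475. CARE-CITE only is 0.804 × 0.525 = 0.42, control only is 0.475 × 0.196 = 0.09, and both is 0.804 × 0.475 = 0.38.

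| d | Power, n=24 | Power, n=12 | CARE-CITE only | Control only | Both |
|---|---|---|---|---|---|
| 0.2 | 16% | 10% | 14% | 8% | 2% |
| 0.3 | 29% | 16% | 25% | 11% | 5% |
| 0.5 | 65% | 35% | 42% | 12% | 23% |
| 0.6 | 80% | 47% | 42% | 9% | 38% |
| 0.8 | 96% | 71% | 28% | 3% | 69% |
| 1.0 | 99.7% | 88% | 12% | 0.3% | 88% |

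**Checks.**
- The direction does not depend on the d chosen: p24(1 − p12) exceeds p12(1 − p24) whenever p24 exceeds p12, which holds for any non-zero common change with equal SDs.
- At d = 0 the two one-sided patterns are equally likely. With 18 dyads per arm they are equal at every d (22% each at d = 0.6).
- Simulated signed rank tests behave the same way: 43.9% v 11.3% at d = 0.5 and 32.3% v 3.0% at d = 0.8.
- In simulations of identical change, the planned two-sample t test is significant in about 5% of cases. Among results significant in CARE-CITE only, it is significant in about 6-8% for d from 0.3 to 0.8, and 15% at d = 1.0. The two readings would therefore usually disagree.
- The 95% interval for mean change excludes zero exactly when the two-sided paired t test gives p < 0.05. Deleting the p-values and keeping the intervals leaves the same pattern visible.

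**The case against.** The strongest reply is that the plan never says it will contrast the two paired results. It plans the right comparison in the next sentence, offers regression to see whether between-arm differences persist, and labels the whole exercise descriptive. The 2:1 split is justified by precision of the estimated changes and by feasibility, so describing within-arm change is a legitimate pilot aim. All of this stands. It makes the point one of interpretation and ordering, not of a missing analysis.

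Three stronger readings are tempting, and the documents do not support them.

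- A reader might infer that improvement from baseline alone would count as success. The baseline clause for Aim 1 refers to effect sizes, not paired p-values, and is joined by 'and' to the control comparison. The formal hypotheses are all against control.
- A reader might apply the 42% at d = 0.6 to all eight retained outcomes and count several spurious patterns. Four of the eight are care-partner scales (CES-D, SF-36, FCCQ-CP, FCCS) and a fifth (FCCQ-SS) is perceived autonomy support. Nothing in the documents implies that these shift through natural recovery. The argument fits MAL, SIS and CAHM.
- A reader might infer that significance in CARE-CITE only is the usual result. That holds near d = 0.5 to 0.6. For small changes the usual result is neither arm significant, and at 0.8 and above it is both.

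The reply leaves one gap. The plan places within-arm change first, writes it into the hypotheses of the analysis section, and does not say that the between-arm comparison decides whether there is an effect.

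**Conclusion.** The point holds as a cheap improvement to the analysis wording. Within-arm change cannot be attributed to CARE-CITE, and with arms of 24 and 12 an identical change in both arms yields discordant paired results that lean toward CARE-CITE. The ratio of the two discordant patterns is about 1.7 to 1 at d = 0.2 (14.0% v 8.2%) and 4.5 to 1 at d = 0.6 (42.2% v 9.3%). It is larger still at d = 0.8 and above, where discordance itself becomes less common.

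These figures assume a two-sided 5% level, equal SD of change and a common change whose size is not in the documents. They apply best to survivor outcomes; for care-partner scales a common trend would have to be assumed. The planned two-sample test is not affected.

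**What to change.** In Data Management and Planned Analysis:

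1. Make the between-arm difference in change the first component of the analysis and the sole basis for any statement of a CARE-CITE effect.
2. Keep each arm's mean change with its 95% interval as description only. Drop the paired p-values or label them as not evidence of effect.
3. Remove the comparison with baseline as a criterion of support, in line with hypotheses 1.1 to 2.2, which are already against control.
4. State that no outcome will be described as improved in one arm and not the other on the strength of arm-specific tests or intervals.

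Item 4 is essential, because removing p-values alone leaves equivalent intervals in place. Allocation, data collection and sample size do not change. The cost is that within-arm p-values, which some readers expect from a pilot, lose prominence. Conclusions will also rest on an imprecise comparison: the 95% interval for the difference has a half-width of 2.03 × √(1/24 + 1/12) = 0.72 SD of change, which is the precision that the design has on the treatment effect.

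### The planned between-arm comparison leaves out each outcome's own baseline score; pre-specifying it for outcomes compared on means would usually tighten the 24 v 12 estimate

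*Combined protocol and SAP*

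**What the plan says.** The Aim 1 and Aim 2 hypotheses are all stated against control. The first reads: "CPs receiving CARE-CITE will have reduced depressive symptoms and improved QOL at 2-month post intervention compared to the control group". Data Management and Planned Analysis repeats the contrast, expecting "more favorable changes in these scores after 3-months as compared to the attention control group". (The documents give the follow-up time as both two and three months. That does not affect this point.)

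The same section firmly plans three things:

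- Within each arm, "construction of 95% confidence intervals in order to summarize changes from baseline to 3-months within each group".
- Within each arm, paired t or signed rank tests.
- Between arms, "we will compare mean or median changes of the outcomes targeted in Aims 1 and 2 across the two groups using two-sample t tests", with Wilcoxon rank sum tests as the alternative when medians are compared.

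Regression is conditional and supplementary: "As needed, we will use linear regression models to augment the primary analyses". That sentence names no specific covariate. The next one lists carepartner age, sex, gender and relationship to the survivor, and then says that "other participant characteristics such as SS other health problems will be examined". The outcome's own baseline score is not named.

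On status, the section says that "these inferences will be viewed primarily as descriptive rather than as definitive hypothesis testing efforts". On timing, Procedures says: "Following baseline data collection obtained via a virtual evaluation by the research evaluator (licensed physical therapist), participants will be randomized to groups". Table 2 collects the outcome measures at baseline and follow-up, and marks the Wolf Motor Function Test as dropped from the remote study.

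**The concern.** Each of the eight retained Aim 1 and 2 scales (CES-D, SF-36, SIS, MAL, FCCQ-CP, FCCQ-SS, FCCS, CAHM) has a pre-randomization score that would be available as a covariate at no extra data cost. A change score uses that baseline in one fixed way: it subtracts it with coefficient 1. If the true slope of follow-up on baseline is below 1, this over-corrects. The estimate then moves with whatever baseline gap the randomization happens to produce, and its variance is larger than it need be.

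The hypotheses turn on the between-arm contrast, and the section on inclusion criteria and recruitment justifies the larger intervention arm by precision. In a descriptive pilot the useful product is the between-arm difference and its interval. The plan names no interval for that difference, and the only comparison it commits to is unadjusted.

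**Working it through.** **Plan's own figures.** The plan gives no figure for between-arm precision. Its only sample-size arithmetic is the enrolment target: 36/0.92 = 39.1, rounded up to 40, which reproduces.

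**Inputs.** From the plan: 24 v 12 complete dyads and a 95% level (stated for within-arm changes only). Assumed: r, the ratio q of follow-up SD to baseline SD, and the slopes. The nearest figure in the documents is the SIS test-retest ICC in Table 2, 0.70 to 0.92. It is not the correlation over the follow-up period and serves only as a rough upper guide to r.

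**Formulas, common slope, in baseline SDs.**

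- SE factor: sqrt(1/24 + 1/12) = 0.354.
- Change-score half-width: t(34) × 0.354 × sqrt(1 + q² − 2rq).
- Adjusted half-width: t(33) × 0.354 × sqrt(q²(1 − r²) × 33/32), where 33/32 is the expected cost of estimating one slope with 36 dyads.

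The reference is the interval implied by the planned two-sample t test.

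| q | r | Change | Adjusted | Adjusted v change |
|---|---|---|---|---|
| 1 | 0.3 | 0.850 | 0.697 | 18% narrower |
| 1 | 0.5 | 0.719 | 0.633 | 12% narrower |
| 1 | 0.7 | 0.557 | 0.522 | 6% narrower |
| 1 | 0.9 | 0.321 | 0.318 | 1% narrower |
| 1 | 0.92 | 0.287 | 0.286 | 0.4% narrower |
| 1.2 | 0.3 | 0.942 | 0.836 | 11% narrower |
| 1.2 | 0.5 | 0.800 | 0.759 | 5% narrower |
| 1.2 | 0.7 | 0.626 | 0.626 | no change |
| 1.2 | 0.8 | 0.518 | 0.526 | 1.5% wider |

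**Largest expected loss against the t interval, common slope.** This occurs when the slope is 1, so that adjustment removes nothing: sqrt(33/32) × t(33)/t(34) = 1.017, or 1.7% wider.

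**Simulation, normal data, q = 1, common slope (20,000 trials per r).** The ratio of empirical SEs, adjusted to change, is 0.82, 0.88, 0.94 and 0.99 at r = 0.3, 0.5, 0.7 and 0.9. Coverage is close to 95% for both methods. These are averages: the adjusted interval is the narrower one in 98.5%, 94.7%, 81.9% and 49.0% of single trials.

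**Unequal slopes (40,000 trials, treated v control).**

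- 0.4 v 1.0: empirical SD 0.245 (change) v 0.249 (adjusted); adjusted coverage 94.1%.
- 0.4 v 0.8: 0.282 v 0.264; adjusted coverage 94.7%.
- 1.0 v 0.4: 0.273 v 0.249; coverage 92.0% (change) v 93.9% (adjusted).

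All estimates are unbiased to within 0.005 SD.

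**Against the rank option.** The estimate that goes with the rank sum test is the Hodges-Lehmann shift on changes. With exponential baseline and residuals (common slope, q = 1, 4,000 trials per r), the empirical SDs, adjusted v rank-based, are:

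- r = 0.3: 0.344 v 0.349.
- r = 0.5: 0.312 v 0.287 (9% larger).
- r = 0.7: 0.251 v 0.218 (15% larger).
- r = 0.9: 0.155 v 0.117 (32% larger).

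A second run gave 0.316 v 0.296, 0.257 v 0.219 and 0.156 v 0.119 at r = 0.5, 0.7 and 0.9. Heavy-tailed t(3) data show the same ordering from r = 0.5 up.

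**Baseline gap.** The chance of a gap above 0.5 SD on one scale is P(|Z| > 0.5/0.354) = 0.157. Such a gap shifts the change-score estimate by (1 − rq) × 0.5 SD, which with q = 1 is 0.35, 0.25, 0.15 and 0.05 SD at r = 0.3, 0.5, 0.7 and 0.9.

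**The case against.** **The planned test is valid.** This stands. A reader might infer from the gap figures that the change-score comparison is biased or wrong. It is unbiased over randomizations, and its interval already covers chance imbalance. The gap probability restates the precision argument and is not a separate harm.

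**The plan already allows adjustment.** This stands in part. A reader might infer that the plan rules out baseline adjustment. It does not: the list of characteristics is open-ended, and the section also plans to look at variables that may influence response. But permission to adjust if needed is not pre-specification, and it leaves the choice of covariate open until the data are in.

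**The gain rests on assumed inputs.** This stands. The 12% to 18% figures need r of 0.3 to 0.5, which the documents neither support nor contradict. If r were as high as the SIS ICC, the gain would be 6% to 0.4%, and with q = 1.2 about zero at r of 0.7 or more.

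**The t interval is the wrong comparator for skewed outcomes.** This stands and limits the point. A reader might infer that adjustment is nearly free for every outcome. The 1.7% bound holds only against the t test. In the exponential case, power for a 0.6 SD shift, adjusted v rank sum, is 0.43 v 0.37, 0.52 v 0.51, 0.66 v 0.72 and 0.94 v 0.97 at r = 0.3, 0.5, 0.7 and 0.9. Replacing the rank analysis for clearly non-normal outcomes could therefore lose precision.

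**A between-arm interval needs no covariate.** True: the interval could be reported for the planned comparison. Its absence is a reason to report one, not in itself an argument for adjustment.

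**Conclusion.** The point holds as a worthwhile improvement to a valid analysis in a descriptive pilot. The only firmly planned between-arm comparison is unadjusted, and each retained outcome has a baseline score taken before randomization.

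For outcomes compared on means, the expected gain over the t interval runs from 18% at r = 0.3 to 1% at r = 0.9, assuming equal SDs, a common slope and roughly normal data. The gain may vanish if slopes differ strongly between arms, or if follow-up SD exceeds baseline SD at high r. Nothing in the documents fixes these quantities, so confidence in the size is moderate. For clearly non-normal outcomes the documents and the calculations do not support displacing the planned rank sum test.

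**What to change.** In Data Management and Planned Analysis, pre-specify the following:

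- **Outcomes compared on means (the t-test branch).** The main between-arm estimate comes from a linear model of the follow-up score (equivalently, the change) on arm and that outcome's baseline score. Report the adjusted difference with its 95% interval. Keep the two-sample t test on changes as a sensitivity analysis.
- **Clearly non-normal outcomes.** Keep the planned rank sum test on changes as the main comparison, with the baseline-adjusted linear model in support.
- **Choice of branch.** The section gives no rule for choosing between mean and median comparisons. State one that does not depend on the between-arm result.

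The within-arm intervals stay as planned, and models with further participant characteristics stay exploratory.

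The cost is a few lines of wording and one degree of freedom per adjusted outcome, with no new data.
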